#### Convergence fusional proximum: (diopters, prism convergence units)

This test is similar to (2) above. When an object is moving closer to our head, the eyes symmetrically converge. When the object is moved beyond the participant's ability to converge, the participant will start to see two images (double vision). This test measures the distance between the bridge of the nose and point where double vision (cm) occurs in seated participants as an object is moved closer.

#### Binocular fusion with divergence: (diopters, prism convergence units)

This is the same test as (3), except that the prisms diverge the light and the participant has to converge their eyes to maintain focus. The score for these tests is simply the maximum amount of prism divergence (diopters, noted on the prism, as one would note diopters on glasses) that the seated participant can accommodate at 3m, and at 30cm.

### Data collection and analysis

At the point of recruitment, a research assistant will describe what is needed of the participant in the study and then the participant will provide informed consent. At the first visit, a research assistant will collect demographic information of each participant. At each visit, the seven orthoptic tests will be administered to the participant by the single clinician (DT) as outlined above. Once each participant has completed their two testing periods, the data will be entered into the patient file by a research assistant. Following, the data will be exported into a comma-separated file for analysis using statistical software. The clinician conducting the orthoptic tests will not be involved in the data extraction or analysis phases.

### Analysis plan

The main objective is to evaluate the agreement and consistency between measurements of the visual system taken at two different times to determine the test-retest reliability of the orthoptic measures. If the tests are perfectly reliable, we would expect the value of the first test to equal the value of the second test for each participant across the range of values for all individuals. The difference between the first and second test for each participant is called the within-group (each participant represents a group) variance. The difference across individuals is the between-group variance. We will assess reliability using the intra-class coefficient (ICC) which measures the between-group variance divided by the total variance (sum of between- and within-group variance). If the within-group variance is 0 (first and second measures are identical), then the ICC = 1 (between-group variance / (between-group variance + 0)). In addition to the ICC, limits of agreement will be estimated using the paired data and illustrated via Bland-Altman plots [18].

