#### *Saccadic movements or oculomotor capacity: (Score = bad, medium, good)*

A light appears on the screen and the participant move their eyes to fix on the object. While they eyes adjust, they will temporarily cover small distances until they achieve a fixed focus. These are called saccadic movements. Lights appear and disappear, in different locations on the screen, at a rate of 100 per minute, lasting 2 minutes. The test result is scored by the evaluator based on a global impression over the entire 2 minutes, with 3 separate sub scores on an ordinal scale for quality (bad, medium, good), for synchronization (bad, medium, good) and saccadic correction (many corrections, few corrections, no corrections). The three sub scores are combined into an overall score according to our industry partner's (Apexk) proprietary algorithm.

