### Sample Size Calculation

Sample size planning is based on the ICC which is our primary outcome. We consider a clinically relevant value in the study population to be ICC  $\ge 0.75$ . Because the measured ICC will vary from sample to sample, we need to consider how precise the estimate of ICC should be. We consider the lower bound of clinical acceptability to be an ICC of 0.5 [19]. Therefore, if the true ICC is 0.75, our estimate precision (95% confidence interval width / 2) must be within 0.25 of the true estimate (0.75 to 0.5). If we include 20 participants, the precision of our ICC estimate

will be  $\pm 0.20$  [19]. This will be slightly more precise than is required, but allows us to account for some potentially missing data or minor technical problems that may occur during the study.

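### If the saccadic score has three levels, Bland-Altman limits are a coarse and sometimes misleading agreement summary; the plan should state the levels and coding and add a cross-table with weighted kappa

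*Combined protocol and SAP*

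**What the plan says.** The protocol describes the saccadic test under the heading "Saccadic movements or oculomotor capacity: (Score = bad, medium, good". The evaluator rates a two-minute recording period by global impression, "with 3 separate sub scores on an ordinal scale for quality (bad, medium, good", with synchronization rated in the same words and saccadic correction on its own three-level scale. Then: "The three sub scores are combined into an overall score according to our industry partner's (Apexk) proprietary algorithm". The number of levels, the range and the numeric coding of that overall score are not given.

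The Analysis plan names one set of methods for the orthoptic measures: "We will assess reliability using the intra-class coefficient (ICC) which measures the between-group variance divided by the total variance", and "In addition to the ICC, limits of agreement will be estimated using the paired data and illustrated via Bland-Altman plots". The saccadic test is not exempted. No kappa, percent agreement or cross-table is planned in any section.

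The Sample Size Calculation makes the ICC the primary outcome and gives a single precision, ±0.20 with 20 participants at a true ICC of 0.75.

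**The concern.** The Analysis plan's objective covers agreement as well as consistency, and limits of agreement are the statistic planned to show agreement. They are usually read as the range that holds about 95% of retest differences. That reading suits a measurement in centimetres or prism dioptres. It suits a three-level rating poorly, because the differences then take only five values and the limits nearly always fall between two of them.

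At stake is how the study reports the reliability of one of its seven tests, and one that rests on a subjective global rating. Limits narrower than one category could leave the impression that ratings hardly change when a fifth of them did. Since the coding is not stated, the person analysing the data would also have to choose it.

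**Working it through.** **Inputs from the protocol.** 20 participants, two visits, planning ICC 0.75, stated precision ±0.20 (Sample Size Calculation). **Assumed, because the documents give none:** three levels, codes 0/1/2, and every table and category share below.

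**1. The plan's own figure.** Large-sample half-width with r = 0.75, k = 2, n = 20:

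1.96 × √[2(1−r)²(1+(k−1)r)² / (k(k−1)(n−1))] = 1.96 × √[2 × 0.0625 × 3.0625 / 38] = 0.197.

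The stated ±0.20 reproduces for a continuous measure. The F-based interval is 0.48 to 0.89, half-width 0.21.

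**2. Limits on a plausible table.** Visit 1–visit 2 pairs: 12 good–good, 3 medium–medium, 1 bad–bad, 2 good–medium, 1 medium–good, 1 bad–medium.

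- Mean difference 0; SD = √(4/19) = 0.459; limits ±1.96 × 0.459 = ±0.90.
- Only the 16 zero differences lie inside: 16/20 = 80%, against a nominal 95%.
- Exact agreement 80%, Clopper-Pearson 95% CI 56% to 94%.
- Chance agreement from the margins (bad/medium/good 0.10/0.20/0.70 and 0.05/0.30/0.65): 0.005 + 0.06 + 0.455 = 0.52.

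**3. How the limits move.** With k one-step changes among 20, split evenly in both directions, the limits are ±1.96√(k/19):

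| One-step changes | Limits | Differences inside |
|---|---|---|
| 2 | ±0.64 | 90% |
| 4 | ±0.90 | 80% |
| 6 | ±1.10 | 100% |
| 8 | ±1.27 | 100% |

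The limits cross one step when k exceeds 19/1.96² = 4.95. Coverage therefore jumps from 80% to 100% as agreement gets worse.

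**4. Same limits, different agreement.** Rows are visit 1, columns visit 2, in the order bad/medium/good.

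- Table A, [7,0,1] [0,3,0] [1,0,8]: 18/20 = 90% exact agreement. The sum of squared differences is 2 × 4 = 8.
- Table B, [4,2,0] [2,4,2] [0,2,4]: 12/20 = 60% exact agreement. The sum of squared differences is 8 × 1 = 8.

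Both have mean difference 0 and limits ±1.96√(8/19) = ±1.27. Unweighted kappa is 0.84 and 0.39.

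**5. The ICC.** For the table in step 2, the between-participant mean square is 2 × 6.80/19 = 0.716 and the within-participant mean square is 2/20 = 0.100. The one-way ICC is (0.716 − 0.100)/(0.716 + 0.100) = 0.755, F interval 0.49 to 0.89. Quadratic-weighted kappa is 1 − 0.20/0.78 = 0.744. The two nearly coincide. Recoding Table B from 0/1/2 to 0/1/3 moves its ICC only from 0.68 to 0.66, but its limits from ±1.27 to ±2.01.

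**6. Caveat on precision.** A simulation of 60,000 studies of 20 people, with the score ICC fixed at 0.75, gave these half-widths for the central 95% range of the estimate: 0.21 for a continuous measure, and 0.22, 0.27, 0.51 and 0.53 for a three-level score with 33%, 60%, 80% and 90% scoring good. The ICC was undefined in 0.3% of studies at 80% good and about 6.5% at 90%.

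**The case against.** The strongest reply is that the criticism of the limits depends on something unknown. The heading's three words may describe the overall score, or may only echo the sub scores, two of which use the same words. A plain sum of three 0–2 ratings would have 7 values, and limits might then be serviceable. This stands, and it is why the point is conditional. Only the request to state levels and coding applies either way.

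Three stronger readings are tempting, and the documents support none of them:

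- *Limits below one step say that nobody changes category.* They are meant to hold about 95% of differences, so they imply change in about 5% or fewer, that is, 1 of 20. The planned plots would also show points outside the limits, although tied points can overlap. The mismatch is 20% against about 5%.
- *The limits say nothing about agreement.* Limits of ±1.10 or ±1.27 in the step series correctly indicate that one-step changes occur and two-step changes are not expected. They are coarse and can understate changes of category; they are not empty.
- *The ICC is the wrong statistic, or cannot be reproduced.* Every equally spaced three-level coding gives the same ICC, and it is close to quadratic-weighted kappa. Only unequal spacing changes it, and only slightly in the example.

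It is also fair to say that one test of seven is affected, that the limits supplement the primary ICC, and that the loss of precision rests on assumed shares. Weighted kappa has the same weakness near the ceiling, so it does not cure that problem.

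**Conclusion.** The point holds in conditional form, as a modest and cheap improvement. The plan does not give the levels or coding of the overall saccadic score and provides no ordinal summary for it. If the score has three levels, the planned agreement statistic can mislead: limits of ±0.90 holding 80% of differences, and identical limits of ±1.27 for 90% and 60% exact agreement. These figures rest on assumed 0/1/2 codes and illustrative tables.

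The ICC remains usable with equally spaced codes. A reader might infer from the simulation that the planned ±0.20 is wrong. It is not: it reproduces for a continuous measure and roughly holds for evenly spread categories. It should simply not be assumed for this score, because healthy volunteers may cluster at good; the documents give no shares. The sample size of 20 and the other six tests are unaffected.

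**What to change.** In the Analysis plan, state the number of levels and the numeric coding of the overall saccadic score before the data are analysed. Then:

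- **If it has three levels:** keep the ICC with equally spaced codes. In place of the limits, report the 3x3 visit 1 by visit 2 table, exact agreement with a 95% CI beside the chance agreement from the margins, and weighted kappa with pre-specified weights. Note that with quadratic weights kappa nearly repeats the ICC and shares its ceiling problem, so the table and exact agreement carry the new information. Do not quote ±0.20 for this measure.
- **If it is a many-level numeric score:** state its range and keep the ICC and limits as planned.

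The cost is a few lines of text, with no extra data or participants. The downside is that this measure is summarised differently from the other six. Exact agreement is not corrected for chance, which is why the chance figure belongs beside it.

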### Sample Size Calculation

Sample size planning is based on the ICC which is our primary outcome. We consider a clinically relevant value in the study population to be ICC  $\ge 0.75$ . Because the measured ICC will vary from sample to sample, we need to consider how precise the estimate of ICC should be. We consider the lower bound of clinical acceptability to be an ICC of 0.5 [19]. Therefore, if the true ICC is 0.75, our estimate precision (95% confidence interval width / 2) must be within 0.25 of the true estimate (0.75 to 0.5). If we include 20 participants, the precision of our ICC estimate

will be  $\pm 0.20$  [19]. This will be slightly more precise than is required, but allows us to account for some potentially missing data or minor technical problems that may occur during the study.

# Safety, Confidentiality and Ethical considerations

# Adverse Events

Participants will undergo the orthoptic visual tests. These tests stress the visual system and can lead to mild test-related symptoms. The clinical experience of our orthoptist is that these symptoms (namely dizziness, mild diplopia or mild headache) occur in a minority of patients, last minutes to hours and resolve by the next day. We consider this an acceptable risk given these tests are used as part of routine clinical management for many diseases, including concussion.

Any participant with persistent increase in symptoms following the test will be contacted the next day to ensure resolution, and will be referred to their treating physician if symptoms persist.

# Serious Adverse Events

As we are only testing healthy adults at two time points, we do not expect any serious adverse events through participation in this study. We have excluded all cases of strabismus (by self-report, and by clinician examination before the tests begin) because it carries a risk of permanent diplopia (double vision) caused by visual orthoptic testing. No other major complications are reported for these tests.

### Premature withdrawal from the study

Any consenting participant has the right to withdraw from the study at any time, for any reason he/she deems relevant. A premature withdrawal from the study will not result in harm to the patient, nor interfere with their normal course of treatment.

# Confidentiality

All collected data will be held anonymously. Participants will be assigned numbers for identification, which will only be accessible to researchers directly involved in the project. Participant addresses and contact numbers will be stored separately from other data and will not be shared with industry partners or any third party. The electronic file will be password protected. Other study data recorded on paper will be in a locked filing cabinet. The information will be kept for a minimum of 7 years following publication of the results by the investigators.

### Ethical considerations

The study will be conducted according to ethical principles stated in the declaration of Helsinki (2013) and will respect any directives determined by the IRB of McGill University. Ethics approval will be obtained before initiating the study. All participants will be able to satisfy all requirements for informed consent; consent forms will take into consideration the well being of all participants, with emphasis on their proper medical follow up and treatment regardless of research objectives, with respect for free-will, human rights and privacy.

